8.1 Primary Endpoint

The primary endpoint for this study will be the proportion of patients achieving a positive response based on the CBR criteria. The CBR criteria consist of six parameters. The CBR and its binary

analysis is described in **Section 7.6 Efficacy Evaluations**. The parameters will be measured as part of standard of care using clinically established scales (e.g. CTCAE version 4.0, May, 2009 grading and Cheson criteria). The primary assessment will occur at 12 ± 1 month. Comparisons will be made to values obtained during the patient's Baseline Visit.

8.2 Secondary Endpoints

The secondary endpoints for this study are (1) the proportion of patients achieving a positive response based on the CBR criteria during intermediate assessment time points, (2) the proportion of patients that remain on study drug for the duration of the study, (3) the proportion of patients that indicate that they are currently receiving sirolimus at the end of the Follow Up Phase, (4) changes in the patient's disease activity, as measured by the CHAP score during intermediate and final assessment time points, (5) changes in the patient's disease activity, as measured by MCD-related Overall Symptom Score as measured by 34 outcome measures during intermediate and final assessment time points and (6) lymph node response, as measured by the Cheson criteria during intermediate and final assessment time points. Comparisons will be made against values obtained during the Baseline Visit.

8.3 Exploratory Endpoints

The exploratory endpoints of this study will be results of correlative studies, in the research laboratory, to investigate the mechanism of action of sirolimus in iMCD and clinical and laboratory biomarkers for treatment response. Additional correlative findings may also be assessed. Spleen size will be measured by radiological imaging (PET/CT or CT).

8.4 Sample Size and Power Determination

Up to 24 subjects may be evaluated under this study, with an interim analysis to be conducted after 14 subjects have completed the Visit 9 intermediate assessment. Additional subjects may be enrolled to increase the degree of precision of the standard error, to a total of 24 evaluable subjects. We anticipate enrolling up to 40 subjects to reach our goal of 24 evaluable subjects.

The difference between enrollment and evaluable accounts for potential subjects that may be deemed ineligible upon screening, or who drop out of the study but are replaced.

Our expected response rate is $\geq 20\%$ versus the null hypothesis of 0% response. The placebo response rate in the only placebo controlled, double blinded clinical trial in iMCD was 0%. Given these parameters, power analysis with type 1 error $\alpha = 0.05$ and power of 1- $\beta = 0.8$ provides a samples size of 14 to determine if sirolimus has activity; the drug will be considered not likely to have a $\geq 20\%$ activity if no responses are seen in the interim analysis.

Sample size was chosen based on (1) convenience and the logistical constraints of recruiting a rare disease population and (2) our intention to probe for a signal of response and understand sirolimus' mechanism of action.

8.5 Statistical Methods

Descriptive analyses will be performed and presented as tables and plots.

Continuous variables: (e.g., age) will be summarized using the following descriptive summary statistics: the number of subjects (n), mean, error, median, minimum value (min), and maximum value (max). For each continuous variable, the corresponding mean, median, minimum and maximum will be presented with error, as determined appropriate.

Categorical variables: (e.g., presence of an AE, gender) will be summarized using counts and percentages.

8.5.1 Efficacy Analysis

CBR will be used as the primary endpoint for assessment of treatment response. Response to drug will be summarized as CBR and its 95% confidence interval and tested using Chi-square (versus historic placebo control data). Difference in CBR in two different study sites will be summarized and compared using the Chi-square tests. Significance will be established at α =0.05.

The baseline covariates will be tested for association with CBR using logistic regression or two-sample t-test and the unadjusted p-values will be reported. When biomarkers are evaluated for association with CBR, we will perform logistic regression analysis for each marker adjusting for possible baseline covariates. The false discovery rate procedure will be used to adjust for multiple comparisons. As an exploratory analysis, if the CBR is not too low, we will also apply the random forest method to evaluate whether such biomarkers cab be predictive to CBR.

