iMCD Idiopathic multicentric Castleman disease HHV-8 Kaposi's sarcoma virus / human herpes virus-8

IL Interleukin

PI3K Phosphoinositide 3-kinase mTOR Mechanistic target of rapamycin VEGF Vascular endothelial growth factor

sIL2R Soluble IL-2 receptor CBR Clinical benefit response

CHAP high sensitivity **C**-reactive protein, **h**emoglobin, **a**lbumin and eastern

cooperative oncology group performance score

CRP C-reactive protein

ECOG Eastern cooperative oncology group

S6K1 p70S6 kinase Eukaryotic translation initiation factor 4E-binding protein 1

4E-BP1 Eukaryotic translation initiation factor 4E-binding protein 1

FKBP-12 FK binding protein-12
EBV Epstein-Barr virus
MTI mTOR inhibitor

FDA Food and Drug Administration

P-gp P-glycoprotein

CYP3A4 Cytochrome P450 IIIA4 GUID Global Unique Identifier

AE Adverse event

SAE Serious adverse event

CTCAE Common terminology criteria for adverse events

eGFR Estimated glomerular filtration rate

ANC Absolute neutrophil count
ALT Alanine aminotransferase
AST Aspartate aminotransferase
HIV Human immunodeficiency virus

CDCN Castleman Disease Collaborative Network

IDS Investigational Drug Service

UAMS University of Arkansas for Medical Sciences

CHOP Children's Hospital of Philadelphia

IP Investigational Pharmacy
CT Computed tomography

PET Positron emission tomography
EDTA Ethylenediaminetetraacetic acid

IRB Institutional Review Board ICF Informed consent form eCRF Electronic case report form

CR Complete response
CRu CR/unconfirmed
PR Partial response
SD Stable disease
PD Progressive disease

SPD Sum of the products of the greatest diameters

DSMB Data Safety Monitoring Board

HMG-CoA 3-hydroxy-3-methyl-glutaryl-CoA reductase

HIPAA Health Insurance Portability and Accountability Act of 1996

PHI Protected health information
LAR legally authorized representative

Definitions:

Eligible Subject A subject deemed to meet all inclusion criteria and not violate any

exclusion criteria.

Enrolled Subject A subject who has provided informed consent to participate in this study.

Anti-IL-6 blockade Siltuximab or tocilizumab

Study Summary

Title	A phase II, single-arm open-label multi-center study of sirolimus in previously treated idiopathic multicentric Castleman disease			
Short Title	Sirolimus in iMCD			
Phase	Phase II			
Methodology	Open-label			
Study Duration	Each subject's participation will last up to 73 weeks. The entire study is expected to last 3 to 3.5 years.			

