3.1 General Design

This study is a Phase II open label study of daily administration of sirolimus in up to 24 evaluable male or female adults. Up to 40 subjects may be enrolled, defined as providing informed consent for the trial, to obtain this target of evaluable subjects. An interim analysis will be conducted after 14 subjects have completed the Visit 9 intermediate assessment. The mechanism of action of sirolimus in clinically active iMCD will also be examined.

Adult subjects will receive a sirolimus loading dose of 5 mg/m², rounded to the nearest mg, on day 1. Loading dose may be lower at the discretion of the prescribing physician. Starting on day 2, adult subjects will take sirolimus daily at 2.5 mg/m²/day (rounded to the nearest mg), adjusted to a target trough level of 10-15 ng/mL. Pediatric subjects will not receive a loading dose, and daily dosing will be at 2 mg/m²/day (rounded to the nearest mg), adjusted to achieve a target trough level of 5-15 ng/mL. (see **Section 5.2, Intervention Regimen**). Given that sirolimus is extensively metabolized by CYP3A4, sirolimus dosing for subjects receiving strong CYP3A4 inhibitors or inducer therapy (https://drug-interactions.medicine.iu.edu/main-table.aspx) should be monitored carefully and adjusted accordingly. Additionally, sirolimus trough levels should be monitored if patients are started on or if their CYP3A4 therapy is altered, and sirolimus dosing adjusted to maintain trough levels of 10-15 ng/mL (5-15 ng/mL in children). The dosing of adult patients who weigh less than 40 kg should be adjusted, based on body surface area, to 3

mg/m² for the loading dose and 1 mg/m²/day daily. It is recommended that the licensed site investigator reduce maintenance dose in patients with hepatic impairment.

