3.1.4 Allocation to Interventional Group

All subjects will receive drug; no randomization will occur.

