4.1 Inclusion Criteria

To be eligible, subjects must meet all of the below inclusion criteria:

- 1. Male or female, age 2-80
- Documented disease history consistent with the diagnostic criteria for iMCD (Appendix 15.1)
 - Confirmation of clinico-histopathological features by licensed pathologist, or a CAS grade of at least 3 in the companion registry study (ACCELERATE)
- 3. Failed/refractory (patient did not achieve sufficient disease control with anti-IL-6 therapy, as determined by the site investigator), relapsed (return of symptoms while on therapy), or inability to tolerate anti-IL-6 or anti-IL-6 receptor therapy
- 4. Evidence of active disease, defined as at least two abnormalities in the criteria comprising the CBR criteria and as defined as abnormal by CTCAE v4.0, including at least one objective measurement (hemoglobin, weight loss, or lymph node size)
 - Hemoglobin < lower limit of normal
 - Fatigue, including fatigue relieved by rest
 - Anorexia, including loss of appetite without alteration in eating habits
 - Fever or night sweats
 - Weight loss ≥ 5% from baseline
 - At least one lymph node meeting modified Cheson criteria (**Appendix 15.2**)
- 5. Ability to consume oral medication in the form of a tablet
- 6. Ability to provide, or for a LAR to provide on their behalf, informed consent prior to any study-specific activities

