7.6 Efficacy Evaluations

The below measures will be used to assess the efficacy of the study intervention and determine if the subject meets criteria for a CBR. All comparisons are against those obtained during the Baseline Visit:

Positive response: Relative to baseline, improvement in at least one of the below criterion without worsening of any single criterion other than hemoglobin on two consecutive study visits.

Negative response: Relative to baseline, worsening of any single criterion other than hemoglobin on two consecutive site visits or failure to achieve improvement for any criterion.

	Hemoglobin	Fatigue	Anorexia	Fever and night sweats	Weight	Lymph node size
Improvement	≥2 g/dL increase without transfusions	≥1 grade decrease by NCI CTCAE version 4.0, May, 2009	≥1 grade decrease by NCI CTCAE version 4.0, May, 2009	≥2°C decrease in fever or return to normal body temperature (37°C) or improvement in night sweats, as assessed by licensed site investigator	≥5% increase not due to increase in new or existing edema	≥25% decrease bi-dimensionally in size of largest lymph node, as measured using Cheson criteria (Appendix 15.2)
Worsening		≥2 grade increase by NCI CTCAE version 4.0, May, 2009	≥2 grade increase by NCI CTCAE version 4.0, May, 2009	≥2°C increase in fever or worsening in night sweats, as assessed by licensed site investigator	≥5% decrease (weight loss not due to decreased edema)	≥25% increase bidimensionally in size of largest lymph node, as measured using Cheson criteria (Appendix 15.2)

The below table provides the CHAP score, which will be used to assess the efficacy of the study intervention. All comparisons are against those obtained during the Baseline Visit:

Score:	0	1	2	3	4
CRP (mg/dL)	<1	≥1, <5	≥5, <10	≥10, <20	≥20
Hemoglobin (g/dL)	≥12	<12, ≥10	<10,≥8	<8	Transfusion dependent
Albumin (g/dL)	≥3	<3,≥2.5	<2.5, ≥2	<2, ≥1.5	<1.5
Performance Score (ECOG)	0	1	2	3	4

The below table provides the modified Cheson response criteria, which will be used to assess the efficacy of the study intervention. Unless otherwise specified, all comparisons are against those obtained during the Baseline Visit:

Complete Response (CR)	All index lesion(s) must have regressed to normal size (≤1.0 cm in		
	their greatest transverse diameter. No new sites of		
	lymphadenopathy >1.5 cm in longest dimension.		
Partial Response (PR)	≥50% decrease in sum of the products of the greatest diameters		

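### The primary test sets open-label CBR, which one symptom item can satisfy, against double-blind historic placebo data, so rating expectancy can be read as sirolimus activity

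*Combined protocol and SAP*

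**What the plan says.** The Study Summary gives the title as "A phase II, single-arm open-label multi-center study of sirolimus in previously treated idiopathic multicentric Castleman disease". Section 3.1.4 adds: "All subjects will receive drug; no randomization will occur".

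Section 8.5.1 reports the CBR rate with a 95% confidence interval and has it "tested using Chi-square (versus historic placebo control data"). It adds "Significance will be established at α =0.05". On the benchmark, Section 8.4 states: "The placebo response rate in the only placebo controlled, double blinded clinical trial in iMCD was 0" percent. The opening of Section 8 sets the null at 0% activity and says the sponsor has access to the historic data.

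Section 7.6 defines a positive CBR as "improvement in at least one of the below criterion without worsening of any single criterion other than hemoglobin on two consecutive study visits". Of the six criteria, fatigue and anorexia improve with a fall of one CTCAE grade. Night sweats improve on the site investigator's judgment, with no grade threshold. Hemoglobin, weight and largest node have numerical thresholds, and Section 6 has scans read centrally.

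Inclusion criterion 4 in Section 4.1 separates the two kinds of item at entry, requiring abnormalities "including at least one objective measurement (hemoglobin, weight loss, or lymph node size"). Neither the response definition nor the test makes that separation.

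**The concern.** In this trial both subject and rater know that active drug is being given. In the historic placebo arm, by the plan's own description, they did not know what was given. One-grade changes in fatigue or anorexia, and a judged change in night sweats, are the items most open to that knowledge, and any one of them can make a responder. The thresholds also lean one way: one grade counts as improvement in fatigue or anorexia, but worsening takes two. The negative-response definition attaches the two-visit requirement to worsening only, so a single unconfirmed improvement may count.

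The chi-square test credits the whole difference from placebo to sirolimus. Section 8 names two limits of the benchmark, stricter enrollment criteria in the historic trial and possible change in standard of care. It does not name blinding, and no analysis in 8.5.1 addresses it. Re-scoring the historic patients by the same CBR definition would align the definitions but not the conditions under which the ratings were made.

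At stake is what a significant primary result could be taken to show.

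**Working it through.** **Inputs from the plan.** Maximum of 24 evaluable subjects and placebo response 0% (Section 8.4); chi-square at 0.05 (Section 8.5.1).

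**Assumptions, because the documents are silent.** The number of historic placebo patients, m, is taken as 20 or 30. The CBR rate that open-label expectancy alone would produce, s, is taken as 5%, 10% or 20%. The test is two-sided, and is shown without and with Yates correction because the plan does not say which applies.

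**The plan's own figure.** The interim number reproduces as a rule-out size: 0.8^14 = 0.044 is below 0.05, while 0.8^13 = 0.055 is not. This is the futility screen and plays no part in what follows.

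**Step 1: responders needed.** For r responders of 24 against 0 of m, the uncorrected statistic reduces to (24 + m) × r × m / [24 × (24 + m − r)], to be compared with 3.841.

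- m = 20: r = 4 gives 44 × 4 × 20 / (24 × 40) = 3.67; r = 5 gives 44 × 5 × 20 / (24 × 39) = 4.70. Five are needed.
- m = 30: r = 2 gives 54 × 2 × 30 / (24 × 52) = 2.60; r = 3 gives 54 × 3 × 30 / (24 × 51) = 3.97. Three are needed.

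With Yates correction the statistic is (24 + m) × [r × m − (24 + m)/2]² / [24 × m × r × (24 + m − r)].

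- m = 20: r = 5 gives 2.86 and r = 6 gives 3.86. Six are needed.
- m = 30: r = 4 gives 3.24 and r = 5 gives 4.63. Five are needed.

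**Step 2: chance that an inert drug reaches that count.** This is P(X ≥ needed) with X binomial (24, s).

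| m | Test | Needed | s = 5% | s = 10% | s = 20% |
|---|---|---|---|---|---|
| 20 | uncorrected | 5 | 0.6% | 9% | 54% |
| 20 | Yates | 6 | 0.1% | 3% | 34% |
| 30 | uncorrected | 3 | 12% | 44% | 88.5% |
| 30 | Yates | 5 | 0.6% | 9% | 54% |

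**Step 3: if placebo CBR is not zero.** Suppose the true placebo rate is 10% and open-label rating adds 10 to 20 points. Summing over both binomials, the chance of a significant excess is 13% to 37% (m = 20) and 19% to 48% (m = 30) uncorrected, or about 5% to 22% and 8% to 32% with Yates. With no added points it is 1% and 3% uncorrected.

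**The case against.** The best reply is that the judgment of activity does not rest on CBR alone. Section 8 says primary and secondary endpoints will both be used, and names the modified Cheson criteria and CHAP. Cheson response depends on node measurements from centrally read scans, and three of the four CHAP items are laboratory values. This stands and narrows the point. It does not answer it, because 8.5.1 specifies no comparison with historic data for either endpoint. Central reading protects only the node item, and any other single item can still make a responder. Section 9.7.2 lets the DSMB adjudicate final outcome, but that is optional and would rest on ratings already made open-label.

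A second reply is that the magnitude is assumed. That also stands: the largest figures need no response at all under blinded placebo and 20% from expectancy alone, and nothing in the documents supports that gap at 12 months in a treatment-refractory population.

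A third is that an open-label, signal-seeking design is openly chosen and the absence of a placebo arm explained. That is accepted. The point concerns only the significance test laid on top of the design.

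A reader might also infer that the interim rule credits expectancy to sirolimus. The documents do not support this. Section 8 presents stopping at 0 of 14 as a way to rule out an inactive therapy; with one or more responses, enrollment may continue in order to estimate the rate better. Passing the screen supports no claim of activity.

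Nor is CBR as a whole investigator-rated. Section 7.6 names the site investigator as rater only for night sweats; hemoglobin and weight are measured.

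**Conclusion.** The point holds for the primary comparison in 8.5.1. Open-label ratings are tested against double-blind placebo data on an endpoint that one symptom item can satisfy, and the plan neither states nor examines the difference. The nominal 0.05 level applies to the drug effect only if open-label rating of an inert drug would yield almost no more CBR responses than blinded placebo did.

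The size cannot be fixed from the documents. Over the assumed values with no placebo responders, the false-positive probability runs from 0.1% to 88.5%, depending on s, m and the continuity correction. This shows a possibility, not an estimate. It would be wrong to infer that a positive result is probably spurious, or that activity cannot be judged at all, since the node-based and laboratory-based endpoints are much less exposed.

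**What to change.** Keep CBR as the primary endpoint and leave the 0-of-14 rule as it is.

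- In 8.5.1, pre-specify a supportive comparison with historic placebo on objective components only: improvement in at least one of hemoglobin, weight or largest node, without worsening in weight or largest node, using the Section 7.6 thresholds. Symptom items should count in neither direction; otherwise open-label ratings could still turn a response negative.
- Apply it identically to both data sets as far as the historic data allow, and say so if a component is missing there.
- Report it beside the full CBR result, with the number of CBR responders who qualified on symptoms alone.
- Add the open-label versus double-blind difference to the benchmark limits in Section 8. Where the objective comparison does not support a CBR difference, interpret that difference with the limit stated.

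The supportive comparison should not become a formal condition for concluding activity, because it has not been powered.

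The cost is analysis-plan wording and one derived variable. It needs no new patients, visits or readers on the trial side; the historic side depends on what those data contain. The comparison will miss subjects whose only benefit is symptomatic, has limited power at 24 subjects, and still needs a judgment on whether weight change reflects edema.

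### With about 5 responders, ordinary logistic p-values for the biomarkers are miscalibrated: after false discovery rate adjustment, likelihood-ratio tests over-declare and Wald tests find almost nothing

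*Combined protocol and SAP*

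**What the plan says.** Section 8.5.1 (Efficacy Analysis) sets out the biomarker analysis in two steps. First, "we will perform logistic regression analysis for each marker adjusting for possible baseline covariates". Then, "The false discovery rate procedure will be used to adjust for multiple comparisons". It does not name the test (Wald, likelihood ratio, penalised or exact), the number or choice of covariates, the number of markers, the false discovery rate procedure or its level. It names no small-sample method.

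The section does recognise that few responders could be a problem, but only for the next step: "we will also apply the random forest method" is made conditional on the response rate not being too low. The logistic models carry no such condition.

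Section 8.4 allows additional enrolment "to a total of 24 evaluable subjects" and expects a response rate of at least 20%. Sections 3.2.3 and 8.3 list biomarkers of treatment response as an exploratory endpoint.

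**The concern.** A false discovery rate procedure takes its p-values as given. If they are too small, the stated error control is lost. If they are too large, the control holds but real associations are discarded. Maximum-likelihood logistic regression relies on large-sample approximations, and about 5 responders must here support an intercept, a marker and one or more covariates. The likelihood-ratio and Wald tests then err in opposite directions, so the result depends on which one the software reports.

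The report could therefore list markers under a nominal 5% false discovery rate when the true rate is several times that. Or it could report that no marker predicts response when the analysis had no realistic chance of finding one.

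**Working it through.** **Inputs from the documents**
- Maximum evaluable subjects: 24 (section 8.4).
- Expected response: at least 20%, so 24 × 0.20 = 4.8, about 5 responders. At a true rate of exactly 20%, the 5th to 95th percentile of the responder count is 2 to 8.
- Significance level: 0.05 (section 8.5.1).

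**Assumptions, because the plan is silent**
- 0 to 4 standard normal covariates; 5, 20 or 100 independent standard normal markers; Benjamini-Hochberg at 5%.

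**The plan's own figure.** Section 8.4 says its calculation "provides a samples size of 14 to determine if sirolimus has activity". This reproduces from the zero-response rule in section 8: the smallest n with 0.8^n < 0.05 is 14 (0.8^13 = 0.055; 0.8^14 = 0.044). It is not in dispute. It says nothing about the biomarker models, which have no sample-size basis of their own.

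**Simulation under the null.** Take n = 24, 5 responders and 20 markers unrelated to response. Fit one logistic model per marker, with p-values from Wald, likelihood ratio (LR) and Firth penalised likelihood ratio, then apply Benjamini-Hochberg. With every marker null, the false discovery rate (FDR) equals the probability of declaring at least one marker.

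| Covariates | LR size | LR FDR | Wald size | Wald FDR | Firth size | Firth FDR |
|---|---|---|---|---|---|---|
| 1 | 7.5% | 14% | 1.7% | 0% | 4.4% | 3.3% |
| 2 | 8.9% | 20% | 1.4% | 0% | 4.2% | 2.0% |
| 3 | 10.7% | 28% | 1.0% | 0% | 4.2% | 1.6% |

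With no covariate, LR size is 6.5% and FDR 10%. With four, they are 13.0% and 42%. In a repeat of the two-covariate case (1,000 simulated trials), LR FDR was 20.1%, with Monte Carlo standard error √(0.20 × 0.80 / 1000) = 1.3 points. A second set-up, with the responder count drawn at 20% instead of fixed, gave LR size 7.9% (one covariate) and 11.9% (three), Wald 1.9% and 1.0%, Firth 4.5% and 4.1%. A further run over 1 to 3 covariates gave LR 7–11%, Wald 0.7–1.7% and Firth 3–4%.

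**Why Wald finds nothing.** With 20 markers the first Benjamini-Hochberg threshold is 0.05 / 20 = 0.0025. In 20,000 null fits with two covariates, the smallest Wald p-value was about 0.017. To reject anything at that value, at least seven of the 20 markers would have to lie at or below 7 × 0.0025 = 0.0175 together.

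**Power with one real marker among 20, two covariates (800 trials each)**

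| Shift in responders | LR power / FDR | Wald power / FDR | Firth power / FDR |
|---|---|---|---|
| 2 SD | 79% / 16% | 0% / 0% | 49% / 4% |
| 3 SD | 99% / 16% | 0% / 0% | 92% / 3% |

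**Sensitivity**
- More responders, 1 to 3 covariates: LR FDR is 9–20% with 8 responders and 10–16% with 12. Wald FDR is 0 in both. Firth FDR is 3–4% in both.
- Number of markers, two covariates: LR FDR is 13% with 5 markers and 35% with 100.
- Complete separation (5 responders, checked by linear programming): 0% with no or one covariate, 0.2% with two, 1.1% with three, 4.7% with four.

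**The case against.** The strongest reply is that the plan leaves the method open and has not chosen a wrong one: it neither names maximum likelihood nor excludes a penalised or exact fit. That is true of the wording. But logistic regression without qualification means maximum likelihood, and each of its two usual tests performs poorly here.

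Five responders is also a floor. The expected rate is at least 20%, and section 7.6 requires improvement in only one of six criteria, without sustained worsening. More responders would reduce the problem, but the likelihood-ratio excess persists even when half the subjects respond. The covariate and marker counts, and the normal, independent markers, are assumptions. Correlated or skewed markers would change the figures. With at most one covariate, likelihood-ratio size is 6.5–7.5%, a modest excess.

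The work is exploratory, and no primary, secondary, interim or safety decision rests on these p-values. That stands and limits the importance of the point.

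A reader might infer more than the documents support:
- **That false discovery rate control fails outright.** It fails with likelihood-ratio p-values. With Wald p-values it held in every setting simulated, and the loss is power.
- **That the trial's mechanism question is compromised.** Section 8 assigns that question to paired comparisons of baseline with later samples by t-test, not to these models.
- **That separation is the main defect.** With 24 subjects and 5 responders it is rare unless several covariates enter.
- **That covariates must be capped at one, or that the random forest plan is at fault.** Firth size stayed at 3.9–4.4% for 0 to 4 covariates in the main simulation, and nothing computed here bears on the random forest.

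**Conclusion.** The concern holds as a minor one. At the planned size the p-values feeding the false discovery rate step are miscalibrated, and the direction depends on a test that the plan does not name. For 1 to 3 covariates and 5 responders among 24, the likelihood-ratio test has true size of about 7–12% at nominal 5%. With 20 null markers it turns a nominal 5% false discovery rate into about 14–28%. Wald has size of about 1–2%, keeps the false discovery rate near 0, and did not detect a real marker even at a 3 SD shift with two covariates.

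These figures rest on the assumed covariate and marker counts, normal and independent markers, and Benjamini-Hochberg at 5%. The direction of the errors was the same in every setting tried. The consequence is confined to the exploratory biomarker-of-response analysis.

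**What to change.** In section 8.5.1, replace logistic regression for the biomarker analyses with Firth penalised logistic regression, using penalised profile-likelihood p-values and confidence intervals. State that these p-values enter the false discovery rate procedure. In the simulations this gave size of about 3–5% and a false discovery rate of 1–4% with 5 responders.

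The cost is a sentence of SAP text and standard software. The downside is fewer nominally significant markers than with likelihood-ratio tests. For unrelated markers with three covariates, the share below 0.05 falls from 10.7% to 4.2%. For a real marker at 2 SD with two covariates, power falls from 79% to 49%, but the higher figure comes with a false discovery rate of about 16%. Against Wald tests, the change is a gain in power.
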